8. STATISTICS

A Statistical Analysis Plan (SAP) will be prepared as a separate document and will include a more technical and detailed description (including templates for Tables, Listings, and Figures) of the planned statistical summaries. The SAP will be finalized before initiating any statistical analysis.

Unless otherwise stated tabulation of summary statistics and data analysis will be performed using SAS[®] Version 9.4 or later.

8.1. Statistical Methods

This study is explorative in nature. Thus, no formal statistical comparisons are planned. Descriptive and inferential statistics will be used to summarize the data. Continuous variables will be summarized by number, mean, standard deviation, median, minimum and maximum values. Categorical variables will be summarized by subject counts and related percentages.

Percentages will be calculated using the total subjects per dose group (Part A), and cohort (Part B).

As a general principle, all summaries from Part A, presented by dose group and Part B, presented by cohort, will be displayed separately. No pooling of data from the two parts is planned.

In Part B (Phase 2a; expansion), cohorts with several defined tumor indications will be treated to detect efficacy signals, in a screening effort to identify tumor indications where CTL-002 has clinically relevant antitumor activity. All indications have been selected based upon translational research results by the sponsor and other scientific groups that indicate an immunosuppressive role of GDF-15 in these tumor indications.

To achieve this and based upon a **conditional probability calculation** the following subject numbers are recruited:

- For the **first group**, for bladder cancer, hepatocellular cancer, non-small cell lung cancer, and melanoma, N = 14 response-evaluable subjects will be initially recruited per each tumor indication. This shall allow to detect 2 responses in a cohort with 80% probability if the true response rate is 20% or more, and at least 1 response in the cohort with 77% probability if the true response rate is 10% or more. For cutaneous squamous-cell carcinoma, N = 12 response-evaluable subjects will be recruited initially. This should result in 2 responses or more with 80% probability if the true response rate is 25% or higher
- For the **second group** (colorectal cancer [MSS/mismatch-repair competent, a currently non-approved anti-PD-1/PD-L1 indication]), N = 10 response-evaluable subject will be recruited. This shall allow to detect 1 response with 89% probability (if the true response rate is 20% or more), and 1 response with 80% probability if the true response rate is 15% or more
- For the **third group** (biomarker cohort with mixed solid tumors; “basket” cohort), N = 75 subjects are planned to be enrolled to have at least N = 25 response-evaluable subjects with TPS PD-L1 > 1 status and ideally up to N = 50 response-evaluable subjects with PD-L1 TPS ≤ 1. For the TPS PD-L1 > 1 group this would ideally confirm a response rate of ≥ 30% (with 81% probability resulting in a minimum of 6 or more responders in the cohort), resulting in a lower limit of the 95% confidence interval of 0.15 (15% lower end response rate), allowing to well rule out background response rates at 5-10% level. For subjects with TPS ≤ 1, a response rate > 20% would be seen as clinically of interest and beneficial, and

this would result in a minimum of 8 (10) responders with a probability of 81% (56%), respectively, if the true response rate is 20% or above. If recruitment of 25 response-evaluable subjects with TPS PD-L1 > 1 is achieved, recruitment into the third group will be stopped and the TPS ≤1 cohort will be evaluated with given patient number in descriptive way.

Response is defined as a subject presenting with a partial or complete response to treatment according to RECIST criteria.

If responses are seen and considered to be of interest by number and depth of response, the SRC may decide in agreement with the Sponsor to expand individual cohorts **following a Simon-2-stage design** to confirm a certain response rate with the following assumptions:

- For the **first group**, for bladder cancer, hepatocellular cancer, non-small cell lung cancer, and melanoma with N = 14 fixed for the first stage, an additional N = 13 subjects may be added to a cohort to achieve at least 4/27 responders and confirms a true response rate of 20% with 80% power. For cutaneous squamous-cell carcinoma, N = 12 fixed for the first stage, an additional N = 24 subjects may be added to a cohort to achieve at least 6/36 responders and confirm a true response rate of 25% with 80% power.
- For the **second group**, for colorectal cancer with N = 10 fixed for the first stage, an additional N = 19 subjects may be added to a cohort to achieve at least 4/29 responders and confirm the true response rate of 20% with 80% power.
- For the **third group** (biomarker cohort with mixed solid tumors; “basket” cohort), with up to N = 75 subjects no such further expansion is considered. Instead, depending on response rate, - depth and - duration observed a potential registration size trial design will be considered and reviewed with the competent authorities (separate protocol). For the PD-L1 TPS > 1 group (“hot” tumors), a response rate of ≥ 30% is seen as clinically of significance, for the PD-L1 TPS ≤1 (“cold” tumors) a response rate > 20% .

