- For the **first group**, for bladder cancer, hepatocellular cancer, non-small cell lung cancer, and melanoma, a minimum of 1 responder each is required to allow for continuation. Treating an additional N = 13 subjects shall generate a total of ≥ 4 responders to assume the overall response rate to be 20% or higher. For cutaneous squamous-cell carcinoma, a minimum of 2 responders is required to allow for continuation. Treating an additional N = 24 subjects shall result in a total of ≥ 6 responders to assume the overall response rate to be 25% or higher
- For the **second group**, for colorectal cancer with N = 10 fixed for the first stage, if at least 1 responder was observed in the first stage, an additional N = 19 subjects may be added to a cohort. In a total of N = 29 subjects at least ≥ 4 responders are expected to assume the true response rate could be at 20% or higher
- For the **third group** (biomarker cohort with mixed solid tumors; “basket” cohort) with up to N = 75 subjects no such further expansion is considered. Instead, depending on response rate, - depth and - duration observed a potential registration size trial design will be considered and reviewed with the competent authorities (separate protocol). For the PD-L1 TPS > 1 group (“hot” tumors) a response rate of ≥ 30% is seen as clinically of significance, for the PD-L1 TPS ≤ 1 (“cold” tumors) a response rate > 20%.

In case of progressive disease (PD), treatment beyond progression might be applied as per Investigator assessment in agreement with the patient.

Proposed indications were selected based upon an **extensive translational research program** by the Sponsor, indicating a negative impact of GDF-15 on the immune response in the tumor microenvironment in the proposed indications, resulting in lack of immune cell infiltration, activation and in some indications proven resistance to checkpoint inhibitor treatment. In all subjects of all cohorts a baseline biopsy is mandatory to evaluate for potential predictive biomarker. In selected cohorts (i.e., melanoma, cutaneous squamous-cell carcinoma and in the

biomarker cohort with mixed solid tumors [“basket” cohort]) sequential, dual tumor biopsies will be taken in subjects with accessible lesions. Enrolment into all cohorts may occur in parallel.

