8.4. Interim Analysis

No formal interim data analysis is planned. However, the Sponsor will review Part A data produced, and based on safety, pharmaco-modelling data, and response data (as far as available), define an initial recommended dose for Part B (Phase 2a; expansion) and to support the submission of the substantial amendment to competent authorities and IEC/IRB. Other summaries of the data may be provided at any point during the study and used to help the Safety Review Committee and the Sponsor make informed decisions.

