8.6. Level of Significance

The level of significance, alpha (α), for this trial is 0.05.

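### Reaching 4/27, 6/36 or 4/29 responders does not confirm a true response rate of 20% or 25%; at one-sided 0.05 it rules out only about 5% (about 8% for cutaneous squamous-cell carcinoma)

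*Protocol*

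**What the plan says.** Section 8.1 sets out three two-stage rules, repeated in the synopsis.

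- **Bladder, hepatocellular, non-small cell lung cancer and melanoma:** the stage sizes read "with N = 14 fixed for the first stage, an additional N = 13 subjects may be added to a cohort". The stated purpose of the expansion is "to achieve at least 4/27 responders and confirms a true response rate of 20% with 80% power". Section 2.1 adds the first-stage gate, "a minimum of 1 responder each is required to allow for continuation", and says of the second stage that it "shall generate a total of ≥ 4 responders to assume the overall response rate to be 20% or higher".
- **Cutaneous squamous-cell carcinoma (CSCC):** the stage sizes read "N = 12 fixed for the first stage, an additional N = 24 subjects may be added". Here the stated purpose is "to achieve at least 6/36 responders and confirm a true response rate of 25% with 80% power". Section 2.1 requires at least 2 first-stage responders.
- **Colorectal cancer:** 10 subjects, then 19 more, with a bar of 4/29 for a rate of 20% at 80% power. Section 2.1 requires at least 1 first-stage responder and words the conclusion more cautiously, as a rate that could be 20% or higher.

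No null rate and no type I error accompany any of these rules. Section 8.6 says on its own that "The level of significance, alpha (α), for this trial is 0.05"; it gives no sidedness and does not mention the two-stage rules.

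**The concern.** A Simon design is defined by a null rate, a target rate, a type I error and a power. A pass rejects the null rate. The power says how often a cohort at the target rate would pass. The protocol gives only the target rate and the power, then attaches the word confirm to the target rate. That reverses the inference.

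The protocol fixes both a decision rule and the conclusion to draw from it, so this is more than a detail left to the analysis plan. Followed as written, a cohort that just reaches its bar would be described as having at least 20% or 25% activity when its observed rate is lower and its interval reaches down to about 4% to 6%. Section 8.5 provides up to 95 subjects for these expansions.

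**Working it through.** **Inputs.** Stage sizes, bars, target rates and power come from section 8.1; first-stage gates come from section 2.1.

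| Cohort | n1 | gate | n | bar | target |
|---|---|---|---|---|---|
| Four group 1 tumors (each) | 14 | ≥1 | 27 | 4 | 20% |
| CSCC | 12 | ≥2 | 36 | 6 | 25% |
| Colorectal | 10 | ≥1 | 29 | 4 | 20% |

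**Formula.** With gate g, bar r and n2 = n − n1:

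P(pass | p) = Σ over x from g to n1 of P[Bin(n1, p) = x] × P[Bin(n2, p) ≥ r − x].

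Equivalently, take the single-stage probability of reaching the bar and subtract the paths that the gate stops.

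**Step 1: reproduce the stated power.**

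- Group 1 at 20%: 0.8177 − 0.0440 × 0.2527 = 0.8066.
- CSCC at 25%: 0.9165 − (0.0317 × 0.5778 + 0.1267 × 0.7534) = 0.9165 − 0.1138 = 0.803.
- Colorectal at 20%: 0.8596 − 0.1074 × 0.5449 = 0.8011.

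All three agree with the stated 80%.

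**Step 2: what the bar is as an estimate.** Observed rate with two-sided 95% Clopper-Pearson limits, the interval named in section 8.3.3:

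- 4/27 = 14.8% (4.2% to 33.7%)
- 6/36 = 16.7% (6.4% to 32.8%)
- 4/29 = 13.8% (3.9% to 31.7%)

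Each observed rate is below the rate it is said to confirm.

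**Step 3: what a pass excludes.** Solve P(pass | p0) = α for p0.

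| Rule | one-sided 0.05 | one-sided 0.025 |
|---|---|---|
| 4/27 | 5.3% | 4.2% |
| 6/36 | 8.2% | 6.9% |
| 4/29 | 5.1% | 4.1% |

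A search over two-stage designs for 5% against 20% (one-sided 0.05, 80% power) returns exactly 10 then 19 subjects with a bar of 4 as the optimal design. This suggests that the colorectal rule was built on a null of 5%, although the protocol does not say so.

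**Step 4: how often a rate below target passes.** At a true 15%:

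- Group 1: 0.5928 − 0.1028 × 0.1180 = 0.581.
- CSCC: 0.4594 − (0.1422 × 0.1394 + 0.3012 × 0.2866) = 0.4594 − 0.1061 = 0.353.
- Colorectal: 0.6513 − 0.1969 × 0.3159 = 0.589.

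**Step 5: sensitivity only.** Section 8.1 names a background of 5-10% for the basket group with PD-L1 TPS > 1. If that range also applied here, the pass probabilities would be:

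| True rate | 4/27 | 6/36 | 4/29 |
|---|---|---|---|
| 5% | 4.2% | 0.6% | 4.7% |
| 10% | 27.4% | 10.5% | 28.9% |

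**The case against.** The best defence is that the numbers are sound and the setting is modest. Section 8.1 calls the study explorative, plans no formal comparisons and describes Part B as a screening effort. Section 8.3.3 already plans Clopper-Pearson intervals, so anyone reading a 4/27 result would see roughly 4% to 34%. This limits the harm. It does not correct the conclusion written into sections 2.1 and 8.1, which a report or analysis plan could carry over unchanged.

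A reader might infer several stronger points that the protocol does not support.

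- **That the rules breach the trial's alpha.** No text ties the 0.05 in section 8.6 to these rules, and its sidedness is not stated. At a true 5% all three pass less than 5% of the time.
- **That 10% is the stated background for these cohorts.** The 5-10% range is given only for the basket TPS > 1 group, whose disease is relapsed on or refractory to anti-PD-1/PD-L1 treatment. Carrying it over is an assumption, and it is weakest for colorectal cancer, where subjects have had no such treatment.
- **That a false success somewhere is nearly certain across cohorts.** Such a figure would require every cohort that clears its gate to expand. Expansion is at the discretion of the Safety Review Committee and the Sponsor, and no claim across cohorts is made.
- **That section 8.4 conceals an interim look.** It says "No formal interim data analysis is planned" but allows data summaries to inform the committee, and section 7.4 describes the expansion decision. The look is disclosed; only its label is open to argument.

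**Conclusion.** The point holds as an error of stated inference. Stage sizes, bars and power need no correction. What does not follow is that 4/27, 6/36 or 4/29 confirms 20%, 25% or 20%. At the bar, the data reject rates up to about 5.3%, 8.2% and 5.1% (one-sided 0.05), and a true 15% still passes 58%, 35% and 59% of the time.

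These results rest on the first-stage gates in section 2.1, on expansion whenever the gate is met, and on a one-sided reading of alpha; the one-sided 0.025 column in the working shows the effect of a stricter level. The central conclusion needs no background rate. The figures at 10% are conditional on an assumption that the protocol does not make for these cohorts.

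**What to change.** In the synopsis and sections 2.1 and 8.1, replace the statements that a bar confirms, or allows one to assume, a rate of 20% (25%) or higher. Say instead what a pass shows: a response rate of about 5% or less (about 8% or less for CSCC) is rejected at one-sided 0.05, with 80% power if the true rate is 20% (25% for CSCC).

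Beside each target rate and power, state the null rate and the one-sided type I error that the sponsor used, and link them to the alpha in section 8.6. The null rates here are back-calculated, so the sponsor should supply its own rather than adopt these by default.

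The cost is text and a more modest claim. Subject numbers, bars and planned analyses are unchanged.

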8.2. Subject Selection for Analyses

The statistical analysis will be conducted in the following data sets:

- The Safety Analysis Set will consist of all subjects who received at least one dose of CTL-002. Subjects will be analyzed according to the dose level initially received
- The PK Analysis Set will consist of all subjects who received at least one dose of study medication and have at least one measurable concentration of CTL-002
- The Efficacy Evaluable Analysis Set as per statistical definition will consist of all subjects who complete at least 2 cycles of treatment (e.g., 1 cycle monotherapy followed by 1 cycle combination therapy for Part A or 2 cycles combination therapy for Part A backfill and Part B subjects), and have baseline and at least one valid post-baseline tumor assessment demonstrating progression or were declared to be clinically progressing or terminated treatment due to a treatment-related AE

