2.2.1.3. Part A (Phase 1; dose escalation)

This study will employ a standard “3+3” dose escalation design for which 3 to 6 subjects will be enrolled at each assigned dose level, per cohort, depending on the occurrence of DLTs.

The planned doses of CTL-002 to be tested are outlined below:

- Cohort 1: 0.3 mg/kg
- Cohort 2: 1.0 mg/kg
- Cohort 3: 3.0 mg/kg
- Cohort 4: 10 mg/kg
- Cohort 5: 20 mg/kg

The start dose of 0.3 mg/kg for Cohort 1 is fixed. Doses explored in Cohorts 2-5 (as outlined above) may be modified by the SRC established for the study based on emerging data (i.e., available safety, PK/pharmacodynamic, other biomarker data).

The DLT Observation Period will be the first 2 treatment cycles (i.e., first 4 weeks) for each dosing cohort. All treatment cycles are defined as 2 weeks in duration. CTL-002 will be administered Q2wk as an IV infusion over 60 minutes. Subjects will first receive one dose of CTL-002 given as monotherapy for one cycle, followed by a combination of CTL-002 given together with the defined anti-PD-1 checkpoint inhibitor for one cycle, where the defined checkpoint inhibitor will be administered at a dose of 240 mg IV given once every 2 weeks infused over approximately 30 minutes.

For the combination, CTL-002 and the defined checkpoint inhibitor will be given on the same day concomitantly, where CTL-002 will always be administered first and for the first combination infusion, there will be a 30-minute observation period to assess safety, which will then be followed by the defined checkpoint inhibitor infusion administered per SmPC or Product Label and local guidelines. The period of observation may be modified (i.e., shortened or lengthened) based on emerging safety data.

The first 2 treatment cycles (i.e., first 4 weeks) represent the DLT Observation Period. Thereafter, subjects will continue with the combination treatment, until progression or until withdrawal from the study for any other reasons (e.g., toxicity or subject withdraws consent).

Additional, intermediate dose cohorts may be explored based on emerging data and upon SRC request. The maximum dose of CTL-002 to be tested in this study will not exceed 20 mg/kg.

All subjects will be hospitalized overnight after receiving the first dose of CTL-002 and also after receiving the first combination dose of CTL-002 and the defined checkpoint inhibitor, for the purposes of safety observation and to enable logistical collection of sampling time-points (e.g., PK).

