The first subject in the next higher dose cohort will not receive treatment with CTL-002 until the previous dose cohort has met the criteria for dose escalation and agreement from the SRC has been obtained and the decision documented in writing.

Intra-Patient Dose Escalation in Extended Treatment

If any Cohort 1 subjects are still on 0.3 mg/kg treatment when Cohort 2 has been completed and reviewed by the SRC, the subjects can be increased to the Cohort 2 dose of 1.0 mg/kg.

If any Cohort 1 or 2 subjects are still on 1.0 mg/kg treatment when Cohort 3 has been completed and reviewed by the SRC, the subjects can be increased to the Cohort 3 dose of 3.0 mg/kg.

Note: Any subjects still on 0.3 mg/kg treatment must be treated at 1.0 mg/kg prior to advancing to 3.0 mg/kg in agreement with the Sponsor Medical Monitor.

The maximum a subject dose can be increased to, through intra-dose escalation, will be 3.0 mg/kg.

Available safety, PK/pharmacodynamic data, as well as preliminary efficacy data will inform the MTD/dose(s) to be further explored in Part B of the study.

The MTD is defined as the highest dose level of CTL-002 at which no more than 1 out of 6 subjects experienced a DLT during the first 2 treatment cycles (i.e., the first 4 weeks, where CTL-002 is given as monotherapy [Weeks 1 and 2] and in combination with the defined checkpoint inhibitor [Weeks 3 and 4]).

In addition, for Cohorts 3-5, in the absence of any DLT, an additional 3 subjects can be recruited into each of these cohorts (up to a total of 6 subjects per cohort), to increase the understanding of the PK and pharmacodynamic data. This occurs while dose escalation continues. These additional “backfill” subjects will receive the combination treatment of CTL-002 and the defined checkpoint inhibitor once every 2 weeks from Cycle 1 Day 1 onwards, with CTL-002 always administered first and the defined checkpoint inhibitor given thereafter as outlined above.

For Part A subjects (except backfill subjects), 3 sequential tumor biopsies are mandated; one biopsy at baseline, the second biopsy prior to the initiation of the combination therapy (after 2 weeks) and the third after the first cycle of combination therapy (either at the End of Treatment visit or, if combination treatment is continued, at the end of Cycle 2/beginning of Cycle 3).

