5.3.4. Recommencement of Dosing

In general, subjects may be considered for recommencement of treatment once

- A toxicity resolves to **Grade ≤ 1** (provided that the toxicity was not recurrent) or
- When a toxicity **is stable and manageable through supportive/medical therapy and in the Investigator’s opinion** and in agreement with the Sponsor Medical Monitor **it appears safe to recommence treatment**

For Part A (Phase 1), CTL-002 recommencement of treatment may be at the initial dose level or one dose level reduced, based upon the discretion of the Investigator ideally in agreement with the Sponsor Medical Monitor. For Part B (Phase 2a) of the study, recommencement of treatment should be at the same dose based upon the discretion of the Investigator ideally in agreement with the Sponsor Medical Monitor. There are no intra-subject dose escalation or reductions allowed. Dosing may only be interrupted, delayed, or discontinued.

For nivolumab, the dose is fixed at 240 mg and no dose adjustment is permitted under any circumstance apart from those provided in the label.

For cemiplimab, the dose is fixed at 350 mg and no dose adjustment is permitted under any circumstance apart from those provided in the label.

Treatment modifications for irAE and infusion-related reactions (Grade 1 to 4) should be handled according to the guidelines in [Section 5.2.5](#).

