8.3.2. Safety Analysis

Summary statistics (mean, median, standard deviation, and range, as appropriate) will be presented descriptively for the following safety endpoints by dose level and overall in Part A and by cohort and overall in Part B. All safety summaries will be presented by dose level (Part A) or cohort (Part B) and visit. The number of subjects experiencing each AE will be summarized by the MedDRA system organ class, MedDRA preferred term, NCI-CTCAE grade, and relationship to study treatment. Serious AEs and irAEs will be summarized separately.

AE summaries:

- Adverse Events - the number of AEs, the proportion of subjects having at least one AE and AEs by MedDRA coded terms will be presented.
- Serious Adverse Events - the number of SAEs, the proportion of subjects having at least one SAE and SAEs by coded terms will be presented.
- Related Adverse Events - the number of related AEs, the proportion of subjects having at least one related AE and related AEs by coded terms will be presented.
- Adverse Events leading to Discontinuation - the number of AEs leading to discontinuation, the proportion of subjects having at least one AE and AEs by coded terms will be presented.

Note: Only treatment-emergent AEs (commencing after exposure to study medication) will be included in the AE summaries. Non-treatment emergent events (starting prior to exposure to study medication) will be included in the subject listings and not included in the above summaries.

Adverse Event Listings:

- Adverse Events, SAEs, DLTs, and AEs leading to discontinuation will also be listed separately
- Details of any deaths will be listed for all subjects
- Any AEs in the study that occur after a subject has received further therapy for cancer (following discontinuation of CTL-002/the defined checkpoint inhibitor) will be flagged in the data listings

Laboratory Evaluations

Clinical laboratory results (including clinical chemistry, hematology, cytokines & chemokines, pharmacodynamic biomarkers, ADA, and urinalysis) will be summarized descriptively by dose level (Part A) or cohort (Part B) and visit, which will also include a display of change from baseline. Listings of abnormal clinical laboratory data according to NCI-CTCAE severity grades (if applicable), abnormal flags (low or high), and clinical significance of the latter will be provided. Shift tables will also be provided tabulating baseline versus on treatment changes in laboratory results.

Vital Signs

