8.3.4. Pharmacokinetic Analysis

Plasma concentrations of CTL-002 will be summarized by dose level (Part A) and cohort (Part B) using descriptive statistics (number of subjects [n], mean, standard deviation, coefficient of variation (CV%), geometric mean, geometric CV%, median, minimum, and maximum by nominal time point. Summary statistics will also be provided for PK parameters by cycle, including but not limited to AUC, C_{max} , and $t_{1/2}$.

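### Part A safety is grouped only by starting dose, although Cohort 1 and 2 subjects may be escalated to 3.0 mg/kg, so later events and laboratory results can carry a dose label up to 10-fold too low

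*Protocol*

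**What the plan says.** Section 8.2 defines the population broadly: "The Safety Analysis Set will consist of all subjects who received at least one dose of CTL-002". It then fixes the grouping: "Subjects will be analyzed according to the dose level initially received". The definitions of the PK and Efficacy Evaluable sets in the same section carry no such rule.

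Section 2.2.1.3 sets the starting doses ("The start dose of 0.3 mg/kg for Cohort 1 is fixed"; "Cohort 2: 1.0 mg/kg") and then permits escalation within a subject during extended treatment. A Cohort 1 subject still on 0.3 mg/kg may move to 1.0 mg/kg once Cohort 2 has been completed and reviewed. When Cohort 3 has been completed and reviewed, for Cohort 1 or 2 subjects then on 1.0 mg/kg, "the subjects can be increased to the Cohort 3 dose of 3.0 mg/kg". The ceiling is 3.0 mg/kg, and a Cohort 1 subject has to pass through 1.0 mg/kg first. The synopsis says the same.

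Section 8.3.2 states: "All safety summaries will be presented by dose level (Part A) or cohort (Part B) and visit". Its AE summaries take in every treatment-emergent event. Its laboratory summaries include cytokines, pharmacodynamic biomarkers and ADA, with change from baseline and shift tables. The only timing flag is for events after further cancer therapy.

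**The concern.** The grouping rule and the escalation rule are both current text, and nothing reconciles them. An event that first appears at 3.0 mg/kg in a subject who started at 0.3 mg/kg is counted as a 0.3 mg/kg event. AEs, laboratory data, vital signs and ECGs are the Part A primary endpoint (section 1.10.1), and pharmacodynamics is a secondary objective (section 1.9.2). A reader who uses the Part A tables to judge how safety or GDF-15 suppression varies with dose would find the two lowest columns containing experience from higher doses, with nothing to show where.

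This is not detail left to the SAP. The protocol states the assignment rule itself, and an SAP that follows it inherits the problem.

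**Working it through.** The plan gives no figure to reproduce. The check sets the rules side by side and works out how large the mislabelling can be.

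**1. Tracing one event.** A Cohort 1 subject reaches 3.0 mg/kg and then has a new AE. It is treatment-emergent, so section 8.3.2 includes it. Section 8.2 groups the subject by starting dose, so it appears under 0.3 mg/kg. No provision moves or marks it.

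**2. Size of the label error** (dose in force ÷ dose in the table).
- Cohort 1 at 3.0 mg/kg: 3.0 / 0.3 = 10.
- Cohort 1 at the intermediate step: 1.0 / 0.3 = 3.3.
- Cohort 2 at 3.0 mg/kg: 3.0 / 1.0 = 3.

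**3. Number of subjects.** Section 2.2.1.3 plans 3 to 6 per cohort, hence 6 to 12 in Cohorts 1 and 2. Section 1.7.1 reports 25 subjects in Part A and no DLT, and backfill was open only to Cohorts 3 to 5. So about 3 per cohort is likely, barring replacements: 2 × 3 = 6, and 6 / 25 = 24%. This is a ceiling, because it assumes that every one of them was escalated.

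**4. Effect of one event.** In a column of 3 subjects, one event in a subject otherwise free of it moves the incidence by 1 / 3 = 33 percentage points.

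**5. Time on treatment needed.** Under section 2.2.1.3 the second subject starts 6 days after the first and the third 2 days later, each with a 4-week DLT period: 6 + 2 + 28 = 36 days per cohort. Assume no gaps between cohorts and instant reviews.
- Cohort 2 completes at 2 × 36 = 72 days. Cohort 1 subjects have then been treated for 72, 66 and 64 days.
- Cohort 3 completes at 3 × 36 = 108 days. Cohort 1 subjects have then been treated for 108, 102 and 100 days.
- Cohort 2 subjects become eligible for 3.0 mg/kg after 108 − 36 = 72, 66 and 64 days.

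Real gaps lengthen these times.

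**6. Mixed cells.** Escalation is triggered by calendar time, whereas tables are by visit. On the same assumptions and 2-week cycles, Cycle 6 falls at 5 × 14 = 70 days from first dose. At that dose the first Cohort 1 subject (eligible from day 72) is still at 0.3 mg/kg, while the other two (eligible from days 66 and 64) may receive 1.0 mg/kg. The next pre-dose laboratory cell would then hold results from two actual doses under one label.

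**7. What is not reached.** The MTD uses only the first 4 weeks (section 2.2.1.4), before any escalation. Escalation stops at 3.0 mg/kg, so no escalated subject belongs to the 10 or 20 mg/kg columns, from which the Part B doses come.

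**The case against.** The strongest reply is that grouping by starting cohort is a legitimate choice. Each subject stays in one column, in line with section 8.1, which bases percentages on all subjects in the dose group. A table by dose at onset has faults of its own. It confounds dose with time on treatment and with selection of subjects who stayed longer. Carry-over also matters: inclusion criterion 15 equates 5 months with five predicted half-lives, about one month each against a 2-week cycle, so an event soon after escalation is not cleanly attributable to the new dose. This stands. It argues for adding a display, not for replacing the present one.

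It is also fair that few subjects may be involved. These were heavily pretreated patients, 6 of 24 evaluable had clinical benefit (section 1.8), the analysis is descriptive, and by-subject listings plus recorded dosing (section 5.6) would let a determined reader rebuild the picture. That limits the impact but does not correct the tables.

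Several stronger inferences are tempting and are not supported:
- **PK is biased.** Section 8.3.4 summarises concentrations by dose level, but the starting-dose rule is not attached to the PK set. Mixing follows only if PK is grouped the same way, which the protocol does not state.
- **Exposure is tabulated under the wrong dose.** Section 8.3.2 names no exposure table.
- **3.0 mg/kg is made to look safer.** Its column keeps exactly Cohort 3's subjects and events. Experience of escalated subjects is not added, but nothing dilutes it.
- **Restarts at a lower dose widen the problem.** Section 5.3.4 says that in Part A "CTL-002 recommencement of treatment may be at the initial dose level or one dose level reduced", but section 5.3.1 says CTL-002 reductions are not allowed. Read literally, 5.3.1 bars CTL-002 escalation too, whereas section 4.1.2 confines the bar to Part B. These passages contradict one another, so the point rests on the explicit escalation provision in 2.2.1.3 alone.

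**Conclusion.** The point holds in a limited form. As the only display of Part A safety, the starting-dose rule puts post-escalation AEs, laboratory results and pharmacodynamic biomarkers under a label up to 10-fold too low for Cohort 1 and 3-fold for Cohort 2. It can inflate the two lowest-dose columns and mix actual doses within a dose-by-visit cell. The number affected lies between none and all of Cohorts 1 and 2, about 6 of 25 on the assumption of 3 per cohort. The protocol does not give the number escalated.

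A reader might infer that dose selection or the tolerability conclusion is at risk. The documents do not support that, for the reasons in the last step of the working. What is lost is a readable dose relation at the lower levels, and that is cheap to restore.

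**What to change.** In sections 8.2 and 8.3.2, or in the SAP with a matching clarification of 8.2:

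- Keep the starting-dose tables as the main display, including for DLTs, disposition and response.
- Add a supplementary Part A summary of treatment-emergent AEs by the CTL-002 dose in force at onset, with time spent at each level. Alternatively, cut or flag events at the first dose change.
- Summarise post-escalation laboratory, pharmacodynamic (including GDF-15) and PK data by the dose actually given, and state the PK grouping explicitly.
- Flag in the listings every subject whose dose changed, and report how many there were.

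Separately, reconcile sections 5.3.1 and 5.3.4, together with 2.2.1.3 and 4.1.2, on whether the CTL-002 dose may change within a Part A subject. Which rule should apply is for the sponsor and investigators to settle.

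The cost is some wording and one extra set of tables. Dosing details are already recorded in the eCRF, so closed Part A enrolment is no obstacle and no new data are needed. The downside is that a subject can appear in more than one column. The added tables should carry a note on carry-over, time on treatment and selection, and should stay supplementary.
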